9.2.1 Treatment-Emergent Adverse Events

The Treatment-Emergent Adverse Events (TEAEs) for SA1, SA2 and the SA-UPA populations are defined as follows.

Part 1 (SA1 population): TEAEs for Part 1 are defined as events that begin either on or after the first dose of the study drug in Part 1 and

- until first dose of study drug in Part 2 if the subject is enrolled into Part 2 or
- until first dose of study drug in the Maintenance Study if the subject is enrolled into the Maintenance Study or
- within 30 days after the last dose administration of the study drug for subjects who are not enrolled in Part 2 and do not participate in the Maintenance Study.

Part 2 (SA2 population): TEAEs for Part 2 are defined as events that begin either on or after the first dose of OL upadacitinib study drug in Part 2 and

- until first dose of study drug in the Maintenance Study if the subject is enrolled into the Maintenance Study or
- within 30 days after the last dose administration of the study drug for subjects who do not participate in the Maintenance Study.

SA–UPA population: TEAEs are defined as events that begin either on or after the first dose of upadacitinib study drug in either Part 1 or Part 2 and

- until first dose of study drug in the Maintenance Study if the subject is enrolled into the Maintenance Study or
- within 30 days after the last dose administration of the study drug in Part 1 for subjects who are not enrolled in Part 2 and do not participate in the Maintenance Study or
- within 30 days after the last dose of the study drug in Part 2 for subjects who are enrolled in Part 2 and do not participate in the Maintenance Study.

If an incomplete onset date was collected for an adverse event, the event will be assumed to be treatment-emergent unless there is other evidence that confirms that the event was not treatment-emergent (e.g., the event end date was prior to the study drug start date). The number and percentage of subjects experiencing treatment-emergent AEs will be summarized.

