Part 2 is an open label, 8-week Extended Treatment Period for subjects who did not achieve clinical response at Week 8 in Part 1. The objectives of Part 2 are to offer upadacitinib induction treatment to placebo clinical non-responders (defined by Adapted Mayo Score) from Part 1, and to evaluate delayed clinical response to upadacitinib in subjects who do not initially respond to upadacitinib during Part 1.

During COVID-19 pandemic, investigators should make the best effort to perform the endoscopies required per protocol. For subjects with missing endoscopy at Week 8/16 when endoscopies cannot be performed due to the COVID-19 pandemic, the site should assess the status of clinical response defined by the Partial Adapted Mayo Score. If the subject is a clinical responder at Week 8/16, the subject may enter Study M14-533 Cohort 1. If the subject is a clinical non-responder at Week 8, the subject may enter Part 2. If the subject is a clinical non-responder at Week 16 the subject will discontinue from the study. A notification should be sent to the TAMD as to the responder status and which part of the program the subject will be going to prior to the transfer taking place.

The blind from Substudy 2 Part 1 will be maintained as these subjects will be assessed simply as non-responders and moved to Substudy 2 Part 2 for further treatment in the study. All eligible subjects entering Part 2 will receive open-label treatment with upadacitinib 45 mg QD for 8 additional weeks (until Week 16).

[figure not shown]
Subjects who achieve clinical response defined by Adapted Mayo Score at Week 8 or Week 16 will be eligible to enroll into Substudy 3. Subjects with missing Week 8 or/and Week 16 endoscopy during the period of COVID-19 pandemic will not be eligible to enter Substudy 3. Subjects who do not achieve clinical response at Week 16 will be discontinued from the study and will not be eligible to enroll in Study M14-533 (long-term extension).

The data collected from subjects in Part 2 will not be part of the primary efficacy analysis for the induction study; descriptive statistics will be used, and the results will be reported separately in the clinical study report.

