5.2.3.4 Rescue Therapy

At or after Week 4 in Substudy 3, subjects who demonstrate loss of response and require medical treatment but have not met the criteria to enter Study M14-533 Cohort 1, may

receive rescue therapy. Rescue therapy may be provided in the form of initiation or increased dosage, at the investigator's discretion, of allowed UC-related medications to treat new or worsening UC symptoms. The allowed UC-related medications are locally acting, oral, or intravenous corticosteroids, aminosalicylates, MTX or UC-related antibiotics.

Anti-diarrheals for control of diarrhea are not considered rescue treatment. Azathioprine (AZA), 6-mercaptopurine (6-MP), cyclosporine, tacrolimus, and thalidomide are prohibited medications during the study and cannot be used as rescue treatment.

Changes in UC-related concomitant medications should be documented in the appropriate eCRF. Rescue therapy should not be withheld even if subject does not meet the criteria for loss of response or before 4 weeks after entering Substudy 3 if in the opinion of the investigator, failure to prescribe them would compromise the subject's safety. Subjects may also be discontinued at any time based on the investigator's medical assessment.

For subjects receiving corticosteroids as a rescue treatment, the investigator is encouraged to initiate tapering based on the subject clinical response status.

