Subjects who complete 52-week treatment in Substudy 3 will enter Cohort 2 in Study M14-533.

Data from Phase 2b and Phase 3 portions of the study will be analyzed separately (i.e., operational seamless) for the efficacy endpoints and will not be combined for statistical inference. For clinical operational efficiency, AbbVie proposes to conduct this seamless Phase 2b/3 study. The operational seamless design is proposed to allow for statistical simplicity where the Type I error controlled is well known.

Rationale of placebo use in this study

A placebo controlled study is necessary for new medication registrational purposes. Based on the guidance provided in the International Conference on Harmonization (ICH) Tripartite Guideline, Topic E10 "Choice of Control Group in Clinical Trials,"³⁴ a placebo-controlled trial design, using randomization and blinding has been implemented in the study in order to minimize subject and investigator bias, and support an objective assessment of all study endpoints. Current EMA guidelines on the development of new medicinal products for the treatment of Ulcerative Colitis (UC)³⁵ state that "unless the study is aiming at demonstrating superiority against an existing treatment, it is critical that assay sensitivity can be demonstrated, ideally by adding a placebo arm." A placebo control is the most objective comparator and a prerequisite for confirmation of clinical benefit in a Phase 3 trial.

In order to minimize the exposure to placebo during the studies, in the induction phase (Substudy 2), subjects will be randomized in a 2:1 ratio to receive upadacitinib or placebo for 8 weeks. If subjects do not respond at Week 8, an open label treatment of upadacitinib 45 mg QD will be provided for an additional 8 weeks. In the maintenance phase (Substudy 3), subjects will have 2/3 chance to be randomized to receive upadacitinib 15 mg or 30 mg QD therapy in Cohort 1, placebo responders (Cohort 2) will continue to

receive placebo, all patients in Cohort 3 and 4 will receive active drug treatment. If patients have loss of response during the maintenance phase, subjects can be enrolled into the open label cohort in long term extension Study M14-533 and receive open label upadacitinib 15 mg QD and possibly with dose escalation to 30 mg QD. Additionally, during the maintenance phase subjects can receive rescue therapy including locally acting, oral or intravenous corticosteroids, aminosalicylates, MTX or antibiotics.

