9.2.1 Treatment-Emergent Adverse Events

The Treatment-Emergent Adverse Events (TEAEs) for SA (SA_A, SA_B, SA_C and SA_D) and SA_UPA populations are defined as follows.

SA (SA_A, SA_B, SA_C and SA_D) population: TEAEs are defined as events that begin either on or after the first dose of the study drug in the Maintenance Study and

- within 30 days after the last dose administration of the study drug for subjects who do not participate in the long-term extension Study M14-533 or
- until first dose of study drug in the Study M14-533 if the subject is enrolled into Study M14-533

SA_UPA population: TEAEs are defined as events that begin either on or after the first dose of upadacitinib study drug in Maintenance Study and

- within 30 days after the last dose administration of the study drug for subjects who do not participate in the long-term extension Study M14-533 or
- until first dose of study drug in the Study M14-533 if the subject is enrolled into Study M14-533

If an incomplete onset date was collected for an adverse event, the event will be assumed to be treatment-emergent unless there is other evidence that confirms that the event was not treatment-emergent (e.g., the event end date was prior to the study drug start date). The number and percentage of subjects experiencing treatment-emergent AEs will be summarized.

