1.0 Introduction

This Statistical Analysis Plan (SAP) describes the statistical analyses for Substudy 2 of upadacitinib Study M14-234, A Multicenter, Randomized, Double-Blind, Placebo-Controlled Study to Evaluate the Safety and Efficacy of Upadacitinib (ABT-494) for Induction and Maintenance Therapy in Subjects with Moderately to Severely Active Ulcerative Colitis.

Study M14-234 comprises 3 substudies: a Phase 2b dose-ranging induction study (Substudy 1), a Phase 3 induction study (Substudy 2), and a Phase 3 maintenance study (Substudy 3). Study M14-234 Substudy 2 examines the efficacy and safety of upadacitinib 45 mg once daily (QD) for induction therapy in subjects with moderate to severely active ulcerative colitis. Throughout this SAP, "Induction Study" is used interchangeably for Study M14-234 Substudy 2, "Maintenance Study" is used interchangeably for Study M14-234 Substudy 3, and "study" refers to Study M14-234.

The analyses of pharmacokinetic endpoints, pharmacodynamic biomarker endpoints and exploratory research and validation endpoints will not be covered in this SAP.

The SAP will not be updated in case of administrative changes or amendments to the protocol unless the changes impact the analysis.

Unless noted otherwise, all analyses will be performed using SAS Version 9.4 (SAS Institute Inc., Cary, NC 27513) or later under the UNIX operating system.

This SAP includes changes to analyses described in the protocol. Details are outlined in Section 13.0.

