11.2.1 Treatment-Emergent Adverse Events

Treatment-emergent AEs during Substudy 1 are defined as events that begin or worsen either on or after the first dose of the study medication in Substudy 1 and within 30 days after the last dose of the study medication in Substudy 1 for subjects who discontinued Substudy 1 and are not enrolled into Substudy 3 or Study M14-533, or events that begin or worsen either on or after the first dose of the study medication in Substudy 1 and up to

the first dose of the study medication in Substudy 3 or Study M14-533. An overview of treatment-emergent AEs, including AEs of special interest such as adverse events leading to death and adverse events leading to early termination, AEs by MedDRA preferred term and system organ class, AEs by maximum relationship to study drug, and AEs by maximum severity will be summarized by number and percentage. Treatment group differences (each ABT-494 dose group versus placebo group, as well as ABT-494 dose groups combined versus placebo group) in the overall incidence of treatment emergent AEs will be assessed with Fisher's exact test for each preferred term for Substudy 1.

The number and percent of subjects experiencing treatment-emergent adverse events will be summarized for the following adverse event categories. Comparisons of the percent of subjects experiencing an adverse event between treatment groups and placebo will be performed using Fisher's exact tests. Only *P* values < 0.100 when rounded to three digits will be presented.

- Any treatment-emergent adverse event.
- Any treatment-emergent adverse event that was rated as possibly related to study drug by the investigator (Reasonable Possibility).
- Any treatment-emergent severe adverse event.
- Any treatment-emergent serious adverse event.
- Any treatment-emergent adverse event leading to discontinuation of study drug.
- Any treatment-emergent adverse event leading to death.
- Any treatment-emergent adverse event of special interest.

Treatment-emergent adverse events will be summarized as follows:

- Grouped by System Organ Class and Preferred Term.
- A by-subject listing will be provided.
- Grouped by System Organ Class, Preferred Term and Severity.
- Grouped by System Organ Class, Preferred Term and Relationship to Study Drug.

- Grouped by System Organ Class and Preferred Term with subject numbers.

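### The Substudy 2 rule for treatment-emergent AEs has no cut-off at the first M14-533 dose, so AEs of responders diverted there under the COVID-19 rule could be counted in Part 1 (placebo included) or Part 2

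*SAP*

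**What the plan says.** **Route out of induction.** Protocol 5.1.1 (repeated in 5.1.2 under the Extended Treatment Period) covers subjects whose Week 8 or Week 16 endoscopy cannot be done because of COVID-19. Response is then judged by the Partial Adapted Mayo score: "If the subject is a clinical responder at Week 8/16, the subject may enter Study M14-533 Cohort 1". The maintenance route is closed to them: "Subjects with missing Week 8 or/and Week 16 endoscopy during the period of COVID-19 pandemic will not be eligible to enter Substudy 3". The rule makes no reference to blinded arm, so it covers placebo responders.

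**Treatment in M14-533.** Protocol 5.2.3.4 ties Cohort 1 to loss of response in maintenance, describing subjects who "have not met the criteria to enter Study M14-533 Cohort 1". Protocol 5.6.1 states that Cohort 1 subjects receive oral upadacitinib, and says of loss of response that "subjects can be enrolled into the open label cohort in long term extension Study M14-533 and receive open label upadacitinib 15 mg QD".

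**TEAE window in Substudy 2.** SAP (Substudy 2) 9.2.1 gives the Part 1 safety population (SA1) three possible ends: first Part 2 dose, first Maintenance Study dose, or 30 days after the last dose "for subjects who are not enrolled in Part 2 and do not participate in the Maintenance Study". The Part 2 (SA2) and all-upadacitinib (SA-UPA) definitions are built the same way. M14-533 is not mentioned in this SAP.

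**TEAE window in the sister SAPs.** SAP (Substudy 3) 9.2.1 runs the window "until first dose of study drug in the Study M14-533 if the subject is enrolled into Study M14-533". SAP (Substudy 1) 11.2.1 runs it up to "the first dose of the study medication in Substudy 3 or Study M14-533".

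**The concern.** A Week 8 responder diverted under the COVID-19 rule enters neither Part 2 nor the Maintenance Study. The only clause of the Substudy 2 rule that fits is the 30-day one, and it keeps running after the subject starts upadacitinib in another study. Taken literally, an event that begins on extension upadacitinib can be a placebo TEAE in the controlled comparison, or an event on 45 mg when the subject is no longer in that treatment period.

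For common events the effect would be slight. For rare events of special interest, such as herpes zoster, thrombosis or serious infection, a single event moved into a planned placebo arm of 154 changes the placebo percentage by 0.65 points (1/154). The direction also matters: active-drug events charged to placebo narrow the safety difference.

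**Working it through.** The plan states no figure on this point, so there is none to reproduce. The check traces the rule and then counts days.

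**1. Tracing a Week 8 COVID-19 responder through the SA1 rule**
- First Part 2 dose: does not apply, because Part 2 is for non-responders.
- First Maintenance Study dose: does not apply, because the missing endoscopy bars entry to Substudy 3.
- 30 days after the last dose: applies. The SAP's Introduction defines the study as M14-234, so the clock starts at the last Part 1 dose.

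A Week 16 responder without an endoscopy meets the same gap in SA2 and SA-UPA. That subject has already had upadacitinib, so the error is one of period and regimen. A placebo responder diverted at Week 8 is not in SA-UPA, having received no upadacitinib in Part 1 or Part 2.

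**2. Whether another rule closes the gap**
- Protocol 8.1.8.1 and 8.1.8.2.1 also use 30 days after the last dose, with no M14-533 stop.
- SAP (Substudy 2) 4.0 assigns safety subjects by most frequent regimen. With 56 placebo days against at most 30 extension days, the subject stays in placebo.
- SAP (Substudy 2) 9.2.4 takes patient-years from study drug exposure, so M14-533 days are not added.

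**3. Length of the overlap.** Protocol 5.1.2 recommends the last Part 1 dose on the day before the Week 8 visit, so about Day 56. The window ends on Day 56 + 30 = Day 86. Extension days inside it are 86 − (56 + gap) + 1 = 31 − gap, where gap is the number of days from the last Part 1 dose to the first M14-533 dose:

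| Gap (days) | Extension days in the Part 1 window | Window end with an M14-533 cut-off |
|---|---|---|
| 1 | 30 | Day 56 |
| 2 | 29 | Day 57 |
| 4 | 27 | Day 59 |
| 8 | 23 | Day 63 |
| 15 | 16 | Day 70 |

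With the cut-off the overlap is zero in every row.

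**4. How many subjects could meet the rule.** Appendix D of the Substudy 2 SAP dates randomisation from 24 October 2018 to 26 May 2020, which is 580 days. Uniform accrual is assumed. The documents do not say when the rule became usable, so two dates are shown:
- Week 8 on or after 29 April 2020 (date of Amendment 5): randomised from 4 March 2020; 83/580 = 14.3%; × 462 = 66.
- Week 8 from late March 2020: randomised from 1 February 2020; 115/580 = 19.8%; × 462 = 92.

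So 66 to 92 subjects reached Week 8 in the relevant period. This is a ceiling for the Week 8 route, since only those who both missed the endoscopy and responded could be diverted. The diversion rate is not in the documents.

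**5. Effect per diverted placebo subject, if the records are merged**
- Planned placebo exposure: 154 × 56/365.25 = 23.6 patient-years.
- Maximum overlap per subject: 30/365.25 = 0.082 patient-years, or 0.35% of 23.6.
- All AEs, at an assumed 200 to 400 per 100 patient-years on extension treatment: 0.16 to 0.33 extra events, adding 0.7 to 1.4 per 100 patient-years to the placebo rate.
- One AE of special interest, at an assumed 5 per 100 patient-years: 0.082 × 0.05 = 0.004 expected events.

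**The case against.** **The effect depends on data handling that the documents do not describe.** M14-533 is a separate study. Appendix C, note e, of the protocol waives the 30-day contact at the end of induction for subjects continuing to M14-533, so their later events would probably be recorded there. A reader might infer that these events will appear in the placebo column. The documents do not support that, because nothing says M14-533 AE records enter the Substudy 2 safety data. This objection stands, and the point is conditional on it. It does not rescue the text: if the records are not merged, the stated 30-day window is not fully ascertained for these subjects.

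**The treatment received is partly inferred.** The explicit open-label statements in Protocol 5.1.2 and 5.6.1 concern loss of response in maintenance. Upadacitinib in Cohort 1 is stated, and open-label use is a reasonable reading. The regimen and start date for a diverted responder are not given.

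**A larger placebo effect is tempting but unsupported.** A reader might assume that 5–20% of the 92 are diverted and that one third are on placebo, giving about 2–6 placebo subjects and 0.7–2.1% of placebo patient-years. The 5–20% has no source, and Protocol 5.3.1.1 first offers a ±7-day window and another facility. The one-third share is the randomisation ratio, whereas diversion selects responders. The protocol plans about 60 subjects in Cohort 2 (placebo responders) against about 525 in Cohort 1, which is 60/585 = 10%. That comparison is crude because the cohorts mix sources, but it points well below one third.

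**It is an edge case.** Substudies 1 and 3 have ordinary routes into M14-533, while Substudy 2 has only the COVID-19 exception. This explains the omission. Leaving M14-533 time out of patient-years is also not special to these subjects, since every subject's 30-day tail is left out. Neither fact supplies the missing cut-off.

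**Conclusion.** The gap is real and no other rule in the protocol or SAP closes it. As written, the Substudy 2 TEAE window for a COVID-19-diverted responder can include up to 30 days on M14-533 upadacitinib, shortened by any dosing gap. Those events would be reported under the Part 1 arm, including placebo, or under Part 2, provided M14-533 AE records are merged with the induction data.

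The likely size is very small. At most about 66 to 92 of 462 subjects (uniform accrual, two assumed start dates) reached Week 8 when the rule could apply. An unknown fraction of them missed the endoscopy and responded, and placebo subjects are probably fewer than one third of those. No placebo headcount or total patient-year share can be taken from the documents. This is a minor correction to the safety rule and does not touch the efficacy conclusions.

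**What to change.** In SAP (Substudy 2) 9.2.1, add to the SA1, SA2 and SA-UPA definitions the clause that the Substudy 3 SAP uses: "until first dose of study drug in the Study M14-533 if the subject is enrolled into Study M14-533". Then limit the 30-day clauses to subjects who enter none of Part 2 (where applicable), the Maintenance Study or M14-533. For an AE starting on the day of the first M14-533 dose, the convention in section 6.0 of the Substudy 1 SAP, which attributes it to M14-533, can be adopted unchanged. One further sentence should say whether M14-533 AE records are used in the Substudy 2 safety tables.

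The cost is a few sentences in the SAP and one date cut-off in the AE program. If the tables have already been produced, a listing by arm of subjects who went from Substudy 2 to M14-533, with AE onset and first M14-533 dose dates, would show whether any event is affected.

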9.2.2 Adverse Event Overview

An overview of AEs will be presented consisting of the number and percentage of subjects experiencing at least one event for each of the following AE categories:

- Any TEAE
- Any TEAE related to study drug according to the investigator
- Any severe TEAE
- Any serious TEAE
- Any TEAE leading to discontinuation of study drug
- Any TEAE leading to death

- TEAEs of Special Interest (as defined in [Appendix B](#))
- All deaths
 - Deaths occurring ≤ 30 days after last dose of study drug
 - Deaths occurring > 30 days after last dose of study drug

In addition, an overview of AEs per 100 patient-years of study exposure will be presented for the AE categories defined above. The number of TEAEs reported, the total number of years of study drug exposure, and the TEAE rate per 100 patient-years will be presented.

9.2.3 Treatment-Emergent Adverse Events by SOC and/or PT

Treatment-emergent adverse events will be summarized by SOC and PT; by maximum relationship to study drug as assessed by the investigator (e.g., reasonable possibility or no reasonable possibility) and SOC and PT; by maximum severity and SOC and PT; and by subject number and SOC and PT. Specific adverse events will be counted once for each subject for calculating percentages, unless stated otherwise. In addition, if the same adverse event occurs multiple times within a subject, the highest severity and level of relationship to investigational product will be reported. The SOC's will be presented in alphabetical order, and the PT's will be presented in alphabetical order within each SOC.

For summary by maximum severity, if a subject has an AE with an unknown severity, then the subject will be counted in the severity category of unknown, even if the subject has another occurrence of the same event with a severity present. The only exception is if the subject has another occurrence of the same AE with the most extreme severity – severe. In this case, the subject will be counted under the severe category.

For summary by maximum relationship to study drug, if a subject has an AE with an unknown relationship, then the subject will be counted in the relationship category of "unknown," even if the subject has another occurrence of the same event with a relationship present. The only exception is if the subject has another occurrence of the same AE with a relationship assessment of "Reasonable Possibility." In this case, the subject will be counted under the "Reasonable Possibility" category.

In addition, treatment-emergent adverse events will be summarized by PT and sorted by decreasing frequency for the upadacitinib 45 mg QD treatment group.

